4.1.3 Selection/Sampling methods

Because the overall study budget restricts the number of cases enrolled, it is necessary to limit enrollment at the largest sites. Because the focus of PERCH is on pathogens responsible for pneumonia mortality we will aim to optimize recruitment of children with very severe pneumonia despite the fact that in most sites they represent a minority of eligible patients. Accordingly we will aim to recruit equal numbers of severe and very severe cases, and therefore the sampling ratio will be higher for very severe cases compared to severe cases (at most sites all very severe cases will be enrolled).

Systematic sampling (e.g. every other case, or enrolling 2 days on/2 days off, or in 8 hour shifts that rotate on different days in which shifts enrollment occurs) will be used to determine which eligible cases will be invited to enroll in PERCH. Systematic sampling will help ensure representativeness since severity and clinical history vary during the day, week and year (more severe cases present at night and on weekends and severity varies seasonally). Because predictability of enrollment eligibility may influence which patients are invited to participate in the study, there is a possibility that patients who present to hospital during enrollment periods may differ from those who present during other times. To minimize selection bias we will

carefully monitor recruitment at each site through screening and tracking of all those eligible, those approached to enroll, and those who consent

Sites will enroll cases throughout the year to obtain seasonal distribution of cases and throughout the week and day, including weekends and evening/nights, to obtain a representative distribution of cases with respect to severity of disease. The enrollment rates will be proportional to the case detection rates, meaning a greater number of cases will be enrolled during peak times and during the high season (see Figure III). A strong study team (rather than regular hospital staff) will manage the detection and selection of cases to help minimize enrollment bias.

[figure not shown]

Figure III. Illustration of case sampling proportional to the case detection rates

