Site	Total Severe* Very severe				
	cases				
Bamako, Mali	700	525	175		
Basse, The Gambia	1170	1016	154		
Sa Kaeo/Nakhon	500	400	100		
Phanom, Thailand					
Soweto/Johannesburg,	2000	1460	540		
South Africa					
Dhaka, Bangladesh	3000	2250	750		

Kilifi, Kenya	1800	1440	360
Lusaka, Zambia	3400	2000	1400
Total	12570	9091	3479

*For sites with unknown ratio of severe to very severe, 25% very severe was assumed.

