6.3.1 Sample size

The target enrollment sample size was based on a series of power calculations and incorporates the need to capture seasonal variations in risk factors for pneumonia and in disease incidence, as well as the cost of testing each subject enrolled. The sample size calculations permit sufficient power to undertake site-specific analyses with a reasonable degree of precision, to conduct sub-analyses of pooled data while controlling for age, season, and site, and to support the identification of novel pathogens.

Cases: Small sites (Bamako, Thailand) will enroll all eligible cases. At the other large sites, sampling of cases will be implemented to restrict the target number of PERCH cases to 6300.

Controls: The target number of controls is based on a minimum background enrollment rate of 25 per month (i.e., 600 over 2 years per site) combined with a 1:1 case:control ratio when monthly case enrollment exceeds the minimum control background rate. For large sites, we anticipate that the overall case:control ratio will be approximately 1:1. For small sites, the overall ratio is anticipated to be slightly higher. For Lusaka and Soweto (i.e., sites with high HIV prevalence), an additional HIV+ control group will be added assuming a 1:1 ratio with the number of enrolled HIV+ cases.

Table XIV. Target case and control enrollment by site and total					
Site	Cases	Controls			
		Community	HIV+ controls		
		Controls			
Bamako, Mali	700	900			
Basse, The Gambia	700	900			
Sa Kaeo/Nakhon Phanom, Thailand	500	600			
Soweto/Johannesburg, South Africa	1200	800	400		
Dhaka, Bangladesh	1200	1200			
Kilifi, Kenya	1200	1200			
Lusaka, Zambia	800	850	350		
Total	6300	7	200		

While PERCH has set a target of 6300 cases to be enrolled, the number actually available may range from 5000-7000. This is due either to losses in data for analysis or higher than projected numbers of cases consenting at some sites. Losses may result from inability to collect and test all specimens, ineligibility due to severe pneumonia signs resolving upon administration of bronchodilators, changes in procedures over time that result in excluding some cases from analysis, and because some sites may not be prepared to start in Jan 2011 (due to minor site capacity development or IRB processes) and thus may not achieve a full 2 years enrollment before the study ends. To account for these potential losses, a low (70%) estimate is provided below.

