Table XV. Target number of cases						
	Target	70% of target				
Site	Total cases	Total cases				
Bamako, Mali	700	490				
Basse, The Gambia	700	490				
Sa Kaeo/Nakhon Phanom, Thailand	500	350				
Soweto/Johannesburg, South Africa	1200	840				
Dhaka, Bangladesh	1200	840				
Kilifi, Kenya	1200	840				
Lusaka, Zambia	800	560				
Total	6300	4410				

HIV-infected cases and controls: Four of the 7 sites have measureable numbers of HIV-infected cases that could be included in an HIV-infected sub-group analysis, either pooled or as a site-specific analysis at the two largest sites. Since HIV status is associated with pathogen infection (i.e., higher carriage in HIV+ than HIV-), and with disease (e.g., higher rates of invasive pneumococcal disease and PCP in HIV+), stratifying analyses by HIV status is desired. Table XV describes the projected number of cases and controls enrolled with HIV. At the two sites with high HIV prevalence (Johannesburg and Lusaka), a second control group of HIV-infected children will be recruited from HIV patient support centers to ensure a sufficient number of HIV+ controls.

Tab	Table XVI. Estimated number of HIV+ cases and controls available in PERCH, by site						
	HIV+	Н	IV+ controls				
Site	cases	community	controls	Total	Assumptions re: HIV prevalence in		
		controls	recruited		cases and community controls		
			from PSCs				
Kilifi	84	24	0	24	7% of cases are HIV+. Assume 2% of		
					children in community are HIV+.		
Soweto	400	40	400	440	5% of U5 are infected and 35% of		
					hosp sev pn are HIV+		
Bamako	63	15	0	15	9% of OP Spn bacteremia were HIV+		
					vs 1.7% controls		
Lusaka	400	50	350	400	30% of children with access to care		
					are HIV+ (assume 50% of sev pn and		
					20% of controls are HIV+)		
Total	947	129	750	879			

Severe versus very severe cases: Because the proportion of very severe pneumonia cases is small compared to severe pneumonia cases, indiscriminant selection may result in insufficient enrollment of very severe pneumonia cases. Therefore, at most sites, all very severe cases will

be invited to participate. At the largest sites, an equal number of severe and very severe cases will be targeted by applying a sampling ratio that is higher for very severe cases.

Table XVII. Target number of severe and very severe pneumonia cases						
	Target		70% of target			
Site	Severe	Very severe	Severe	Very severe		
Bamako, Mali	525	175	368	123		
Basse, The Gambia	526	174	368	122		

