Sa Kaeo/Nakhon Phanom, Thailand	400	100	280	70		
Soweto/Johannesburg, South Africa	660	540	462	378		
Dhaka, Bangladesh	900	300	630	210		
Kilifi, Kenya	840	360	588	252		
Lusaka, Zambia	400	400	280	280		
Total	4251	2049	2976	1434		

Number of cases available by age group: Assuming the age distribution of cases is 50% 1-11m, 30% 12-23m, and 20% 24-59m, the estimated number of cases by age group per site and overall are provided in Table XVII.

Table XVII. Estimated number of severe and very severe pneumonia cases by age

	Target			70% of target		
Site	Total	Severe	Very	Total	Severe	Very
	cases		severe	cases		severe
Bamako, Mali	350	263	88	245	184	61
Basse, The Gambia	350	263	87	245	184	61
Sa Kaeo/Nakhon	250	200	50	175	140	35
Phanom, Thailand						
Soweto/Johannesburg,	600	330	270	420	231	189
South Africa						
Dhaka, Bangladesh	600	450	150	420	315	105
Kilifi, Kenya	600	420	180	420	294	126
Lusaka, Zambia	400	200	200	280	140	140
Total	3150	2126	1025	2205	1488	717

(A) age 28 days-11 months

(B) age 12-23 months

	Target			70% of Target		
Site	Total	Severe	Very	Total	Severe	Very
	cases		severe	cases		severe
Bamako, Mali	210	158	53	147	110	37
Basse, The Gambia	210	158	52	147	110	37
Sa Kaeo/Nakhon	150	120	30	105	84	21

Phanom, Thailand						
Soweto/Johannesburg,	360	198	162	252	139	113
South Africa						
Dhaka, Bangladesh	360	270	90	252	189	63
Kilifi, Kenya	360	252	108	252	176	76
Lusaka, Zambia	240	120	120	168	84	84
Total	1890	1275	615	1323	893	430

(C) age 24-59 months

	Target			70% of Target		
Site	Total	Severe	Very	Total	Severe	Very
	cases		severe	cases		severe
Bamako, Mali	140	105	35	98	73	25
Basse, The Gambia	140	105	35	98	74	24
Sa Kaeo/Nakhon	100	80	20	70	56	14
Phanom, Thailand						
Soweto/Johannesburg,	240	132	108	168	92	76
South Africa						
Dhaka, Bangladesh	240	180	60	168	126	42
Kilifi, Kenya	240	168	72	168	118	50
Lusaka, Zambia	160	80	80	112	56	56
Total	1260	850	410	882	595	287

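### Dhaka's case target in Table XVII (900 severe, 300 very severe) ignores severity and is 300 very severe cases short of the protocol's equal-numbers sampling rule

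*Protocol*

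**What the plan says.** Protocol 4.1.3 (Selection/Sampling methods) gives the aim for sites where enrolment must be limited: "Accordingly we will aim to recruit equal numbers of severe and very severe cases", to be reached by sampling the very severe group at a higher ratio. It adds that at most sites every very severe case will be enrolled, and it gives the reason: the study is about pathogens that cause pneumonia deaths.

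Protocol 6.3.1, under severe versus very severe cases, warns that selection blind to severity could yield too few very severe cases. It then sets two routes. One is general: "Therefore, at most sites, all very severe cases will" be invited. The other is for big sites: "At the largest sites, an equal number of severe and very severe cases will be targeted by applying a sampling ratio that is higher" in the very severe group.

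Three tables give the Dhaka figures:

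- Table XIII, available over two years (total, severe, very severe): "Dhaka, Bangladesh 3000 2250 750". Its footnote reads: "For sites with unknown ratio of severe to very severe, 25% very severe was assumed".
- Table XIV, target cases and community controls: "Dhaka, Bangladesh 1200 1200".
- Table XVII, target severe and very severe, then 70% of each: "Dhaka, Bangladesh 900 300 630 210".

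**The concern.** Dhaka has the second-largest pool of available cases (3000, after 3400 at Lusaka) and shares the highest case target (1200, with Soweto and Kilifi). On either measure it is one of the largest sites, so equal numbers would be expected. Its target instead keeps the 3:1 mix of the available cases.

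Two things are at stake. First, text and table imply different sampling ratios for the same site, while protocol 4.2.1 says a valid analysis needs a known selection probability for every eligible child. Second, the Dhaka row feeds the pooled severe and very severe totals, the 70% columns and the three age-by-severity tables, and disease severity is a listed subgroup analysis in 6.3.

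**Working it through.** **1. Reproduce the Dhaka row.** Severity-blind allocation of 1200 cases:

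- severe: 1200 × 2250/3000 = 900
- very severe: 1200 × 750/3000 = 300

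Both match Table XVII exactly. The column totals, 4251 and 2049, also reproduce, so the table adds up. The problem is its conflict with the rule.

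**2. Sampling fractions at every site.** Fraction = Table XVII target / Table XIII available.

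| Site | Severe | Very severe | Route met |
|---|---|---|---|
| Bamako | 525/525 = 100% | 175/175 = 100% | all very severe |
| Thailand | 400/400 = 100% | 100/100 = 100% | all very severe |
| Soweto | 660/1460 = 45% | 540/540 = 100% | all very severe |
| Kilifi | 840/1440 = 58% | 360/360 = 100% | all very severe |
| Basse | 526/1016 = 52% | 174/154 = 113% | all very severe, but target exceeds availability |
| Lusaka | 400/2000 = 20% | 400/1400 = 29% | equal numbers |
| Dhaka | 900/2250 = 40% | 300/750 = 40% | neither |

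Dhaka is the only site where cases are sampled and the very severe fraction is not the higher one.

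**3. Size of the shortfall.**

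- Equal numbers: 1200/2 = 600 of each. Shortfall 600 − 300 = 300. Fractions become 600/2250 = 26.7% and 600/750 = 80%; 750 − 600 = 150 very severe cases remain unsampled.
- All very severe, if Dhaka is not counted as a largest site: 750 very severe and 450 severe. Shortfall 450.
- Pooled totals under 600/600: severe 4251 − 300 = 3951; very severe 2049 + 300 = 2349 (+14.6%); sum still 6300. The 70% figure for very severe goes from 1434 to 1434 + 210 = 1644.

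**4. Feasibility.** Equal numbers need 600 very severe cases, and 600/3000 = 20%. Dhaka's 750/3000 is exactly 25%, the default in the Table XIII footnote. The protocol does not say which sites were imputed.

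**5. Effect on power.** The protocol gives no power for Dhaka by severity, so this scenario is an assumption built on its settings: OR 2.0, two-sided alpha 0.01, and the 1200 Dhaka controls. With case prevalence p1, control prevalence follows from odds0 = [p1/(1 − p1)]/2, so p0 = 5.26% for p1 = 10% and p0 = 3.09% for p1 = 6%. Power = Φ[(p1 − p0 − 2.576·SE0)/SE1], with SE0 the pooled and SE1 the unpooled standard error.

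| Dhaka cases vs 1200 controls | p1 = 6% | p1 = 10% | p1 = 15% |
|---|---|---|---|
| 300 | 44% | 65% | 82% |
| 600 | 63% | 86% | 96% |
| 900 | 74% | 93% | 99% |

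Moving from 900/300 to 600/600 lifts very severe power from the first row to the second and lowers severe power from the third row to the second. Using the unpooled standard error throughout, very severe power goes from 28% to 54% at 6% and from 49% to 80% at 10%: same direction, larger gain. Pooled very severe power (2049 or 2349 cases against 7200 controls) is above 99.8% at 6% either way.

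**The case against.** **The rule is soft.** Section 4.1.3 states an aim, the all-very-severe route applies only at most sites, and the largest sites are never named. This stands as a comment on the drafting but does not remove the conflict. If Dhaka is one of the largest sites it misses equal numbers; if it is not, it misses the other route by more. No exception for Dhaka is stated, and an equal fraction in both groups does not meet the aim even partly.

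**The 750 may be assumed.** This stands. The 600/600 target is feasible only at a very severe share of 20% or more, and at 25% it means enrolling 80% of a pool already reduced for consent.

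**The loss can be overstated.** A reader might infer that the mismatch leaves 450 of 750 very severe cases unsampled. Under the equal-numbers rule 150 of those would be unsampled anyway, so the shortfall is 300. A reader might also infer that the protocol's stated power is wrong. It is not: the figures in 6.3.3.1 rest on total cases, and at its 15% benchmark prevalence even 300 very severe cases give 82% by the pooled-variance formula (71% unpooled). The gain also has a price, the lower severe-case power at Dhaka.

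**It may be too late to change the sampling.** The document is version 6.0 of November 2013, and section 2.3 plans enrolment from January 2011 to April 2013, although 6.3.1 allows for late-starting sites. The documents do not show whether the text or the table reflects how Dhaka was meant to be sampled. This also stands, and it is why the request is to reconcile the two.

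**Conclusion.** The contradiction is real. Table XVII plans Dhaka at 40% of each severity group, which conflicts with 4.1.3 and 6.3.1, and Dhaka is the only site that follows neither route. Against equal numbers the target is 300 very severe cases short, on two assumptions: Dhaka counts as one of the largest sites, and at least 20% of its available cases are very severe.

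The practical effect is local. It touches the Dhaka very severe count, severity comparisons at that site, and the projections built on the row. Pooled detection of very severe associations is hardly affected, and the documents do not support a claim that the study as a whole is underpowered because of it. The restated pooled totals also still contain Basse's target of 174 against 154 available, a separate discrepancy.

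**What to change.** Reconcile the sampling rule with the table in one of two ways.

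1. **Apply the rule.** Set Dhaka to 600 severe and 600 very severe within the same 1200. The pooled totals become 3951 and 2349, before any correction of the Basse row. Update the 70% columns (Dhaka 420/420) and the three age tables (Dhaka 300/300, 180/180 and 120/120, using the protocol's 50/30/20 age split). State whether Dhaka's 750 is observed or the 25% default.
2. **State the exception.** Say in 4.1.3 and 6.3.1 that Dhaka is sampled without regard to severity and that its planned very severe count is 300.

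If enrolment at Dhaka is already complete, state the severity-specific sampling fractions actually used and carry them into the analysis.

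The second route costs a sentence in each section. The first costs table edits and a changed sampling ratio at one site, with 300 fewer severe cases there (severe power 93% to 86% at 10% prevalence, 74% to 63% at 6%). Neither adds patients to the target.

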6.3.2 Post Mortem Sample Size

Overall PERCH aims to capture at least 6000 patients at 7 sites. The mortality rate will vary between sites (estimated to be between 1-5%), and this would translate to approximately 350 deaths. Operating at 5/7 sites and assuming a consent rate of no greater than 50%, this would mean a total potential of 5-50 fatal cases for biopsy for each site for 18 months with a maximum total sample size of ~ 150 cases. This may be nearer 75-100 cases if consent is lower (which may be the case), but a sample size of even 100 (lower end of expectations) would be realistic to answer the basic question of whether the microbiology results are interpretable, whether the histology is additive, and whether molecular diagnostics have any utility.

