The Zambia PERCH study site will be located at University Teaching Hospital (UTH), a 1500-bed academic center and tertiary care facility with 425 pediatric in-patient beds located in the capital city, Lusaka and the home of Zambia's only medical school. In 2008 there were a total of 14,923 in-patient pediatric admissions, 3467 (23%) of which were ARI and 1035 (30%) occurred in children under 5 years old. The case fatality rate of severe pneumonia was 25.8%. UTH serves the greater Lusaka District, an area of 70 square kilometers and a population of 1.3 million. National per capita income (USD 395) is half that recorded at independence in 1964 and among the world's lowest. Consistent problems include: extreme poverty, overcrowding; poor access to water and sanitation (26% with flush toilets); food insecurity and high unemployment (9% formally employed). These conditions and a poor public health infrastructure contribute to one of the world's highest rates of pneumonia (59.5/1000 children) and pneumonia mortality. HIV (19% seroprevalence among women attending ante-natal clinics) and tuberculosis (506 cases per 100,000) are severe problems highly affecting the burden of pulmonary disease in Lusaka.

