4.2.4.4 Study Aims

- 1. Detect infections or co-infections missed during antemortem evaluations
- 2. Validate antemortem diagnosis
- 3. Assess the correlation of histopathological patterns of disease with etiology, particularly if novel pathogens are involved.
- 4. Improve diagnosis of pulmonary tuberculosis and pneumonia-like conditions

- 5. Interpret pathology results in conjunction with clinical data, as the lack of such an analysis has been a limitation of previous studies.
- 6. Form a biorepository for future investigations in this field.

The PERCH project is investigating the etiology of childhood pneumonia in seven different countries. PERCH plans to study the clinical course and determine the microbiological causes of pneumonia in children from 1 month to 5 years old. As part of the PERCH study, we will study tissues from the lung in patients who die of pneumonia in six of these study sites (excluding the Gambia), dependent on the outcome of local IRB approval. A full open autopsy is often difficult to perform for a number of reasons, so we plan to use postmortem percutaneous needle biopsies of the lung.

All PERCH cases will be monitored throughout their hospital stay. The parents of any fatal pneumonia case participating in the study will be approached for participation before or after death depending on the site customs, preference, and community acceptability.

4.2.4.5 **Post Mortem Inclusion criteria**

Cases must meet the following inclusion criteria for eligibility to enter into the PERCH lung biopsy study:

- Enrolled in the PERCH study
- Patient dies in hospital
- Not more than 12 hours have elapsed since death
- Parental/guardian consent given for lung biopsy

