4.5.1.9 Post mortem Lung biopsy

Post-mortem lung biopsy will be obtained for microbiological, histological and immunocytochemical evaluations in order to establish the etiology in fatal cases of pneumonia, validate ante-mortem etiologic diagnosis of fatal pneumonias and asses the correlation of histopathological patterns of disease with etiology, particularly if novel pathogens are involved. Full open autopsy is not being considered, as it is unlikely to be acceptable to parents in the majority of sites. Instead PERCH proposes to collect limited amounts of lung material by percutaneous tru-cut needle biopsy from several sites in the lung using a standardized protocol. These samples would be collected within a 4-hour time frame after the child's death, with the consent of relatives. Timing of the collection of the post mortem lung biopsy is important as delays in obtaining the specimens will increase the risk of contamination and add "noise" to the results. Please refer to section 4.2.4 for more details.

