5.6.1 Post Mortem Risk Assessment Considerations

All safety considerations are for the staff who will be handling the lung biopsy specimens. The procedures outlined above must comply with local standards. It is important to note that all tissue samples must be handled as if potentially infectious.

Special care must also be taken for approaching parents for consent. Because all care-takers will be under significant emotional distress, staff will be trained to approach all potential participants in a respectful manner.

Post-mortem studies in research settings have typically recorded acceptance rates of up to 25% (4). Families may decline consent for a variety of reasons – religious or cultural objections, concerns about mutilation of the body, interference with burial arrangements, perception that procedure is of no benefit to the patient, objections expressed by patients before death and perception that patient is too young or too old (12, 13). Taking a biopsy approach confined to the lungs may allay some of these fears, for example, about scarring or delay in burial arrangements.

We aim to take the biopsies as soon as possible after death allowing for the interval of the consent process, but preferably within 4 hours of death (ideally 1-2 hours) in order to reduce interference with the normal arrangements for dealing with the body (transport to a mortuary or funeral rites etc). This would also ensure optimal tissue quality and the least chance of post mortem microbiological contamination.

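### Section 6.3.2: the expected deaths, maximum and lower end given for the post-mortem biopsies do not follow from the section's own inputs

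*Protocol*

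**What the plan says.** Section 6.3.2 begins with the case count: "Overall PERCH aims to capture at least 6000 patients at 7 sites". It continues: "The mortality rate will vary between sites (estimated to be between 1-5%), and this would translate to approximately 350 deaths". It then applies 5/7 of the sites, consent no higher than 50% and a period of 18 months. From these it derives 5–50 biopsies per site and a maximum of about 150 in total. It adds that the total may be nearer 75–100 if consent is lower. It concludes that "a sample size of even 100 (lower end of expectations" would be enough to show whether the microbiology is interpretable, whether histology adds to it, and whether molecular tests are useful.

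Other sections bear on the same inputs:

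- **Sites.** Section 4.2.4.4 plans biopsies "in six of these study sites (excluding the Gambia".
- **Consent.** Section 5.6.1 says earlier post-mortem studies "typically recorded acceptance rates of up to 25" per cent. Section 8.3 expects that up to 50% may decline.
- **Mortality.** The Zambia entry in section 3.2 reports: "The case fatality rate of severe pneumonia was 25.8" per cent.
- **Cases and period.** Section 6.3.1 gives a target of 6300 and a possible range of 5000–7000. Section 2.3 gives two years of enrolment at each site.
- **Timing of biopsy.** The inclusion criteria in section 4.2.4.5 require: "Not more than 12 hours have elapsed since death". Section 4.5.1.9 says: "These samples would be collected within a 4-hour time frame".

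**The concern.** The section gives a short chain of multiplications, and a reader who repeats it gets different answers at each step: the deaths, the per-site yield, the maximum and the lower end. The lower end matters most. The only argument that the sub-study is large enough is that even 100 biopsies would do, so if 100 is not a floor, that argument has no support as written.

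Sections 4.2.4.1 and 4.2.4.4 intend the biopsies to validate ante-mortem diagnoses. Section 4.2.4.1 adds that they may help extrapolate from less specific specimens to the surviving cases. A reader planning that work needs to know whether to expect some tens of biopsies or well over a hundred.

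**Working it through.** **Inputs.** Cases N: at least 6000 (6.3.2); target 6300, range 5000–7000 (6.3.1). Mortality 1–5% (6.3.2). Biopsy sites 5/7 (6.3.2) or six (4.2.4.4). Consent at most 50% (6.3.2). Site targets 500 to 1200 (Table XIV).

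**Formulas.** Deaths = N × mortality. Biopsies = deaths × share of sites × consent. The 18-month column multiplies by 18/24. That assumes biopsy runs for 18 of the 24 enrolment months with deaths spread evenly; the section does not show how it used the 18 months.

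| N | Deaths, 1–5% | Biopsies, 5/7 × 50% | Same, × 18/24 | Biopsies, 6/7 × 50% |
|---|---|---|---|---|
| 5000 | 50–250 | 17.9–89.3 | 13.4–67.0 | 21.4–107.1 |
| 6000 | 60–300 | 21.4–107.1 | 16.1–80.4 | 25.7–128.6 |
| 6300 | 63–315 | 22.5–112.5 | 16.9–84.4 | 27.0–135.0 |
| 7000 | 70–350 | 25.0–125.0 | 18.8–93.8 | 30.0–150.0 |

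**The 350 deaths.** 350/6000 = 5.8% and 350/6300 = 5.6%, both above the stated ceiling of 5%. Only 7000 × 5% = 350 reproduces it.

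**The maximum of about 150.** From 350 deaths with the section's own factors, 350 × 5/7 × 0.5 = 125. The figure of 150 appears as 350 × 6/7 × 0.5, with six sites, or as 300 × 0.5, with no site factor; neither includes the 18/24 factor. Choosing the five largest sites does not rescue it. They hold 5100 of the 6300 target cases, so 5100 × 0.05 × 0.5 = 127.5, or 127.5 × 7000/6300 = 141.7 if enrolment reached 7000.

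**Per site.** Smallest: 500 × 0.01 × 0.5 = 2.5. Largest: 1200 × 0.05 × 0.5 = 30. The section says 5–50.

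**The lower end of 100.** With N = 6000, five sites and 50% consent, 100 biopsies need mortality of 100/(6000 × 5/7 × 0.5) = 4.7%. Over 18 of 24 months they need 4.67%/0.75 = 6.2%, outside the stated range. At 7000 cases the 24-month figure is 100/2500 = 4.0%. With six sites and 6000 cases it is 100/(6000 × 6/7 × 0.5) = 3.9%. In each case 100 sits in the upper part of the 1–5% range or beyond it.

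**Effect of the conflicting inputs elsewhere.**

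- *Case fatality at the Zambia site.* If 25.8% applied to its 800 target cases, that site alone would have 800 × 0.258 = 206 deaths. Adding 1–5% of the other 5500 cases (55–275) gives 261–481 deaths. Multiplying by 5/7 × 0.5 gives 93–172 biopsies, or 70–129 with the 18/24 factor.
- *Acceptance of 25%.* 60–300 deaths × 5/7 × 0.25 = 11–54 biopsies.

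These two move the yield in opposite directions.

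**The case against.** Several parts of the case for the protocol stand. The section says at least 6000, and with the 7000 allowed in section 6.3.1 the 350 deaths can be reached. It is therefore an upper-end figure presented as the expected one, not an impossible one. The six sites in section 4.2.4.4 give exactly 150, so one unreconciled site count may explain the maximum, although the intent cannot be proved. The section also hedges its figures, and the sub-study is descriptive: no test, precision target or enrolment target depends on the count.

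A reader might infer that the sub-study will be much smaller than stated. The documents do not support that. The Zambia case fatality would raise the yield enough to bring 350 and 150 within range, although it is reported beside 2008 hospital admissions and is not a forecast for enrolled cases.

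A reader might also take the 25% acceptance as contradicting the 50%. It describes earlier post-mortem studies. Section 5.6.1 goes on to say that a biopsy confined to the lungs may ease some objections, and section 8.3 expects it to be more acceptable than open autopsy. What does remain is that section 6.3.2 uses 50% as a ceiling on consent, whereas up to 50% declining in section 8.3 makes 50% a floor.

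Finally, a reader might see the 12-hour and 4-hour limits as a flaw in specimen quality. Section 5.6.1 states a preference for within 4 hours, so 12 hours can be read as the eligibility limit and 4 hours as the aim. Section 4.5.1.9 is worded more firmly, so the wording should agree, but this has no bearing on the sample size.

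**Conclusion.** The stated figures are wrong as written. From the section's inputs, deaths are 60–300 (70–350 at 7000 cases) and biopsies about 21–107 (25–125 at 7000 cases). Over 18 of 24 months with even accrual, which is an assumption, the range at 6000 cases is about 16–80. The approximately 350 deaths are the extreme upper end, the maximum of about 150 is not reached with five sites, and 100 is close to the top of the computed range rather than its lower end.

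The direction of the net error is unknown until site count, consent, mortality and period are settled. The finding is that the adequacy statement is unsupported, not that the sub-study is too small. The main case-control sample size and power calculations are not touched.

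**What to change.** Rewrite section 6.3.2 as follows:

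1. State one number of biopsy sites, five or six, and name them consistently with section 4.2.4.4.
2. State one consent range and reconcile it with sections 5.6.1 and 8.3.
3. Give mortality by site, and explain how 1–5% relates to the Zambia figure in section 3.2.
4. Say how the 18 months enter the calculation.
5. From the site targets in Table XIV, tabulate deaths and biopsies per site, and give the total as a range with its lower end and maximum.
6. Base the adequacy statement on that lower end rather than on 100.

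Separately, reconcile the wording on time since death in sections 4.2.4.5, 4.5.1.9 and 5.6.1.

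The cost is one paragraph, a small table and a wording check. No design change is needed.
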